# 4.4.7 Statistical/Analytical Issues

# 4.4.7.1 Adjustments for Covariates

The MMRM or ANCOVA model (depending on the endpoint) to compare treatment groups during Double-Blind Treatment Period will include a covariate adjustment for the baseline parameter value of interest.

# 4.4.7.2 Handling of Dropouts or Missing Data

Treatment groups will be compared for observed and change from baseline in weekly WI-NRS score during the Double-blind Treatment Period using a MMRM to include fixed effects for treatment, type of cholestatic disease (PBC, PSC), week, and treatment by week interaction, with the relevant baseline value included as a covariate. A similar model will be used for the exploratory analysis of bi-weekly WI-NRS scores, replacing the week score with a bi-weekly score in the model.

As a sensitivity analysis of the primary endpoint, subjects missing data will be imputed using MI methodology using the subjects in the Full Analysis Set. The MI will be performed under the assumption data is missing at random (MAR) using the model defined in the primary analysis. Using the general methodology described in Ouyang (2017), the following imputations will be applied:

- Intermittent missing value(s) arising prior to a discontinuation event (i.e., discontinuation of randomized treatment or early permanent dropout) are imputed using the Markov Chain Monte Carlo (MCMC) option in SAS PROC MI by treatment group assuming nonmonotone missing, a seed of 671982, 500 burn-in iterations, 100 iterations between imputations, and a non-informative prior. The MAR assumption is reasonable for intermittent missing values as the values of the endpoint before and after the intermittent missing value are known. The imputation of the intermittent missing data will be accomplished using the MCMC option in SAS PROC MI to impute intermittent missing data without a monotone missing pattern, prior to performing imputations of values following the discontinuation event.
- Missing data following a discontinuation event will then be imputed by treatment group under the assumption of MAR using the regression option from the monotone statement of SAS PROC MI. The baseline and post-baseline derived weekly visits during the Double-Blind Treatment Period will be used in the regression option to impute the missing values.
- The MI methods described above will be used to generate 30 imputed datasets. Data will be analyzed using the primary MMRM model for the observed and imputed data; observed and change from baseline values to each post-baseline week visit will be calculated based on observed and imputed data.

 Results from the analysis of each of the 30 imputed datasets will be combined using Rubin's imputation rules (Rubin 1987) through SAS PROC MIANALYZE to produce pooled LS mean estimates of treatment difference.

For assessment of responder endpoints, subjects with missing data at the time point of interest will not be analyzed (i.e., PGI-C, PGI-S and WI-NRS); only observed values will be used.

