#### **11.1.1. Worst Itch Numeric Rating Scale (WI-NRS)**

Subjects will be asked to rate the severity of their worst level of itching in the past 24 hours in the morning, and at the same time of day, using the WI-NRS. The WI-NRS is an 11-point scale ranging from 0 (No Itching) to 10 (Worst Itching Imaginable) ([Phan 2012](#)) and requires approximately 1 minute to complete. Higher scores indicate greater itch severity. Itching severity scores collected via the WI-NRS have been categorized in the literature as mild (<4), moderate ( $\geq 4$  to <7), or severe ( $\geq 7$ ) ([Fishbane 2020](#), [Hirschfield 2020](#), [Levy 2020](#), [Stander 2020](#)). An example of the WI-NRS is included in [Appendix B](#).

Subjects will be instructed to complete the WI-NRS daily, in the morning, and at the same time of day, beginning at Day -14 to the Follow-Up Visit. For days that coincide with a study visit (for Visit 2 and beyond), the WI-NRS is to be completed before the visit.

The WI-NRS scores from Day -7 through Day -1 will be averaged together to confirm compliance and determine subject eligibility for continued participation regarding pruritus sensation. The average WI-NRS score using the daily values from the week before the first dose of study drug (Visit 2 [Day 1]) will serve as the baseline score. The 7 daily WI-NRS scores prior to Visit 6 (Week 6) will be averaged together for primary endpoint analyses. Data from at least 4 of the 7 days for each week are required to be considered an acceptable profile.

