- Within the Open-Label Extension Period, analysis of Week 7 will be the first 7 days after the nominal Week 6 visit date or start date of open-label dosing, whichever is later; for subjects who participate in the decentralized model, there may be a gap between the nominal Week 6 visit and open-label dosing due to drug shipment considerations. Subsequent analysis visits will be counted using the next 7 days. The Week 6 WI-NRS score will be used as the Initiation of OLE score.

The Safety Follow-up Period will be anchored to the nominal Week 12 visit date. Week 13 will be the first 7 days after the nominal Week 12 visit date and Week 14 will be derived using the next 7 days.

For subjects who early terminate during the Double-Blind Treatment Period, the subject's first day of dosing (i.e., study day 1) will be the anchor date for weekly analysis visit derivations. Week 1 will be study days 2 through 8 and subsequent weekly analysis visits will be the next 7 days, deriving all applicable analysis visits until early termination.

The following additional general considerations will be applied in deriving the weekly WI-NRS scores:

- No WI-NRS daily score is to be utilized in more than one analysis visit derivation.
- For weeks where 7 calendar days are available for a given week, there must be 4 non-missing daily scores to compute the weekly score; if more than 3 daily scores are missing, the weekly score is considered missing.

• For weeks where less than 7 calendar days are available for a given week due to visit anchoring rules, at least 57% of the daily scores for the available calendar days must be reported, maintaining the same rate of reported scores as seen for a full week (i.e., 4 out of 7 days). If 6 calendar days are available for a given week, 4 non-missing daily scores are required. If 4 or 5 calendar days are available for a given week, 3 non-missing daily scores are required. If less than 4 calendar days are available for a given week, the weekly score will be considered missing.

A bi-weekly WI-NRS score will be calculated for exploratory analysis. The average WI-NRS score using the daily values from the 14 days before the first dose of study drug (including the WI-NRS score captured on the study day 1 of dosing) will serve as the baseline bi-weekly score.

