# 4.1.3 Summarization by Visit

Assessments that are collected only at study visits (i.e., all study assessments except WI-NRS) are to be summarized by study visit and will be based on the nominal, scheduled visit label as reported on the eCRF.

Subjects who discontinue from the study early will have their assessments conducted at the early termination visit mapped and summarized with the next scheduled nominal visit, according to the schedule of events, based on the last visit completed per protocol.

Any subject who completes the Open-Label Extension Period or discontinues study drug (EP547 or placebo) early will complete a Follow-Up Visit (Visit 9) approximately 2 weeks (±3 days) after the last dose of study drug. The Follow-Up Visit may be summarized in both the Double-Blind Treatment Period and Open-Label Extension Period summaries, based on the treatment period of participation at the time of study termination or completion and as warranted by available data.

Data collected at unscheduled visits will not be included in by-visit summaries, but will be considered when endpoint derivations potentially include multiple visits (e.g., determination of baseline value, determination of worst post-baseline value, etc.). All data will be included in subject listings.

For details on WI-NRS analysis visits, see Section 3.4.1.1.

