# 4.4.4.2 Responder PGI-C Analysis

The proportion of subjects with improvement at Week 6 will be compared among treatment groups using a Cochran-Mantel-Haenszel (CMH) chi-square test, stratified by the type of cholestatic disease (PBC, PSC). The PGI-C responses at each visit in the Double-Blind Treatment Period (i.e., Week 6) and Open-Label Extension Period (i.e., Week 12) will also be presented with the number and percentage of subjects in each response category by treatment group along with two-sided 95% Clopper-Pearson exact CIs. Proportional endpoints (PGI-C, PGI-S and WI-NRS) will be analyzed using the number of patients in each treatment group with non-missing data at each visit (i.e., observed values) as the denominator for percentages for the Double-Blind Treatment Period and Open-Label Extension Period summaries.

[figure not shown]

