# 4.4.5 Exploratory Endpoint Analysis Methods

# 4.4.6 Sensitivity Analysis of Efficacy Endpoints

Sensitivity analyses of the primary endpoint will be conducted to better assess the impact of intercurrent events on the efficacy conclusions. The intercurrent events of interest include receipt of prohibited and/or rescue medications while on study and early withdrawal of study drug. The treatment policy strategy will be used for the primary estimand.

The while on treatment strategy will be used as a sensitivity analysis to further explore the intercurrent event of prohibited and/or rescue medication usage. The difference in means between treatment groups in the weekly WI-NRS score at the last visit prior to receipt of prohibited and/or rescue medications (or the last derived weekly WI-NRS score, for those who never require prohibited and/or rescue medication) will be presented during the Double-Blind Treatment Period. For those subjects that receive a prohibited and/or rescue medication, any WI-NRS scores reported after the receipt of medication will be excluded from the analysis.

Determination of intercurrent events based on use of a prohibited and/or rescue medication will be based on review of the Concomitant Medication eCRF. Before study unblinding, the sponsor will review all reported concomitant medications, including onstudy changes to background medications, to determine which qualify as an intercurrent event for prohibited or rescue medication usage. This external assessment will be documented in the study files and integrated into the sensitivity analysis.

The analysis of the primary efficacy endpoint will be analyzed for the Full Analysis Set using multiple imputations (MI) assuming data missing at Week 6 to be missing at random (MAR) (Section 4.4.7.2), and for the Per Protocol Set using observed data.

Treatment group comparisons will use the methodology described in Section 4.4.3 for sensitivity analysis of the primary endpoint.

Secondary and PD endpoint analyses during the Double-Blind Treatment Period will be repeated for the Per Protocol Set as supportive analyses.

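### The six responder secondary endpoints are tested on observed cases with no missing-data check, and early-termination PGI-C, PGI-S and 5-D values can be analysed as Week 6 weeks before Day 43

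*SAP*

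**What the plan says.** SAP 3.4.1.2 lists seven secondary efficacy endpoints. Six are proportions: PGI-C improvement, PGI-S improvement, WI-NRS reduction of at least 2, 3 or 4 points, and WI-NRS below 4. The seventh, 5-D, is continuous.

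- **Responder analysis.** SAP 4.4.4.2 computes percentages "using the number of patients in each treatment group with non-missing data at each visit (i.e., observed values) as the denominator for percentages". SAP 4.4.4.3 and 4.4.4.4 apply the same method to PGI-S and WI-NRS. SAP 4.4.7.2 repeats the rule: "subjects with missing data at the time point of interest will not be analyzed".
- **Sensitivity analyses.** The imputation is introduced this way: "As a sensitivity analysis of the primary endpoint, subjects missing data will be imputed using MI methodology". The while-on-treatment analysis in SAP 4.4.6 also concerns the primary endpoint. For the rest, SAP 4.4.6 says: "Secondary and PD endpoint analyses during the Double-Blind Treatment Period will be repeated for the Per Protocol Set as supportive analyses".
- **Early-termination questionnaires.** Under SAP 4.1.3 these are "mapped and summarized with the next scheduled nominal visit, according to the schedule of events, based on the last visit completed per protocol". WI-NRS is handled elsewhere.
- **WI-NRS of early terminators.** SAP 3.4.1.1 counts weeks from the first dose, "deriving all applicable analysis visits until early termination". A short week has its own rule: "If less than 4 calendar days are available for a given week, the weekly score will be considered missing". Under Protocol 11.1.1 the diary is completed daily, "beginning at Day -14 to the Follow-Up Visit".
- **Schedule.** Protocol Appendix A has no visit between Week 3 (Day 22) and Week 6 (Day 43), each with a window of 3 days either side. It marks 5-D, PGI-C and PGI-S at the early-termination visit.

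**The concern.** If missing Week 6 status is related to response and losses differ between arms, a comparison of observed cases is biased, and the bias can go either way. The plan examines this for the primary endpoint and for none of the six responder endpoints. The Per Protocol Set removes subjects for deviations (SAP 4.2), which is a different question. A subject with WI-NRS scores for Weeks 1 to 5 but not Week 6 contributes to the primary model and is imputed at Week 6 in its sensitivity analysis, yet drops out of all four Week 6 WI-NRS responder tests.

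The mapping raises a second problem. A PGI-C, PGI-S or 5-D value taken soon after Week 3 can be analysed as a Week 6 value, while WI-NRS for the same subject follows study days. Week 6 results shown side by side may therefore rest on different subjects and on measurements taken at different times.

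**Working it through.** **1. Expected loss.** SAP 4.6 assumes about 10% withdrawal: 26/0.9 = 28.9, rounded up to 29 per arm, and 29 × 0.9 = 26.1 completers. The plan's figure reproduces. It implies 29 − 26 = 3 missing per arm, six of 58.

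Six is a planning rate, not a bound. Diary gaps can add WI-NRS losses, since more than 3 missing days void a full week (SAP 3.4.1.1). Retention after stopping drug (Protocol 8.5.1) and mapped early-termination questionnaires can reduce the losses.

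**2. Effect on a responder comparison.** Response rates are not given, so these are assumptions: 15 v 9 responders of 29 (EP547 v placebo), every missing subject a non-responder, unstratified two-proportion z-test with pooled variance.

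| Missing, EP547/placebo | Comparison | Difference (points) | p |
|---|---|---|---|
| Missing as non-response | 15/29 v 9/29 | 20.7 | 0.110 |
| 3/3 | 15/26 v 9/26 | 23.1 | 0.095 |
| 4/2 | 15/25 v 9/27 | 26.7 | 0.054 |
| 5/1 | 15/24 v 9/28 | 30.4 | 0.029 |
| 1/5 | 15/28 v 9/24 | 16.1 | 0.246 |

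Probability of 5/1 or more extreme in that direction:
- Equal risk per arm: (6 + 1)/64 = 10.9%.
- Six drawn at random from the 34 non-responders (14 v 20): [C(14,5) × 20 + C(14,6)]/C(34,6) = 3.2%.

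The planned test is stratified. With an assumed 23 PBC and 6 PSC per arm and responders 12+3 v 7+2, the Cochran-Mantel-Haenszel p-value (no continuity correction), taken over all allocations of the losses to strata, is:
- missing as non-response: 0.116
- 3/3: 0.077 to 0.120
- 4/2: 0.045 to 0.063
- 5/1: 0.025 to 0.032

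So 4/2 sits on the 0.05 line in the stratified test.

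**3. Non-response coding is not neutral.** Assume 12/29 true responders per arm.
- If all missing are non-responders, the spurious observed-case difference is 0 at 3/3, 12/25 − 12/27 = 3.6 points at 4/2, and 12/24 − 12/28 = 7.1 at 5/1.
- If three would-be responders are lost from one arm, observed cases give 9/26 − 12/29 = −6.8 points. Missing as non-response gives 9/29 − 12/29 = −10.3.

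**4. How early a mapped value can be.** Gap = 43 − (day of last completed visit + 1).
- Visit 5 on Day 22: 43 − 23 = 20 days. On Day 19 or Day 25: 23 or 17 days.
- Exit on Day 42: 1 day.
- After Visit 4 (Day 15) or Visit 3 (Day 8), the literal next visit is Week 3 or Week 2, where these questionnaires are not scheduled. If the rule is read as the next visit that collects them, the gap is 43 − 16 = 27 or 43 − 9 = 34 days.

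**5. Where PGI and WI-NRS part company.** For an early terminator, Week 1 is Days 2 to 8, so Week 6 is Days 37 to 43. At least 4 calendar days are needed, so the diary must reach Day 40. Take Visit 5 on Day 22.
- If early termination means the termination visit, exits on Days 23 to 39 have a mapped Week 6 PGI value but no Week 6 WI-NRS score.
- If it means the end of the diary, about 14 days after the last dose, a last dose on Day 26 already reaches Day 40. Only last doses on Days 22 to 25 are affected. With the follow-up visit 3 days late or early, this becomes Day 22 only, or Days 22 to 28.

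**The case against.** These are unadjusted secondary endpoints in a single-dose proof-of-concept study, and only the primary endpoint is error-controlled (Protocol 14.12). Four of the six are cut-points of the primary variable, whose missing data are covered by the mixed model and by multiple imputation. Limiting the imputation to the primary endpoint matches Protocol 14.8.3. N, n and disposition are tabulated by arm (SAP 4.1.1, 4.3.1), so responders over N can be worked out by hand. At the planned balanced loss the conclusion does not change. All of this stands and keeps the priority modest. It does not supply a test or interval that covers every Full Analysis Set subject.

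The meaning of the early-termination cut-off for WI-NRS is a weaker point. Protocol 9.4.5 ties the Early Study Termination Visit to leaving the study and checks the diary up to it, which favours the termination-visit reading. Subjects who stop drug but attend Week 6 are anchored to that visit, so few are affected.

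A reader might infer three stronger claims:
- **That the responder results will favour EP547.** The documents give neither response rates nor a reason to expect unequal loss, and the bias can run either way.
- **That six missing is a ceiling, or 20 days a maximum or typical gap.** Neither holds, as steps 1 and 4 show.
- **That every Week 6 questionnaire value outside Days 40 to 46 is suspect.** For completers, the questionnaires carry the nominal visit label and WI-NRS is anchored to the same visit date, so the two agree.

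**Conclusion.** The concern holds in two limited parts. First, none of the six responder endpoints has a planned analysis that examines missing data. Second, SAP 4.1.3 allows PGI-C, PGI-S and 5-D values to enter Week 6 between about 1 and 23 days before Day 43 after Visit 5, and about 27 or 34 days before it if exits after Visit 4 or Visit 3 are also read as Week 6. The same subject can then be observed for PGI and missing for WI-NRS.

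The likely numerical effect is small. With balanced loss in the assumed example it is 2.4 points (23.1 − 20.7), with no change of conclusion. Crossing 0.05 in the unstratified test with six missing needs a 5/1 split or worse, at 3 to 11%. These figures rest on assumed rates, on every missing subject being a non-responder, and on six missing in total. Neither the observed-case rule nor the questionnaire mapping touches the primary endpoint. The change is worth making because it is cheap and the rules are best set before unblinding.

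**What to change.** Before unblinding:

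1. Keep the observed-case analysis. Add a sensitivity analysis that derives Week 6 WI-NRS responder status for all Full Analysis Set subjects from the 30 imputed datasets already planned. Compute a Mantel-Haenszel risk difference stratified by PBC/PSC in each dataset and pool by Rubin's rules.
2. Add a labelled sensitivity analysis that counts missing Week 6 PGI-C and PGI-S as non-response. State that mapped early-termination values are treated as missing in it, and that it can increase bias if would-be responders are lost.
3. Add a sensitivity analysis of Week 6 PGI-C, PGI-S and 5-D that excludes only mapped early-termination values collected before the Week 6 window (before Day 40, from 43 − 3). Leave completers' nominal Week 6 values unchanged.
4. As accompanying wording, state in SAP 4.1.3 how early-termination values after Visit 3 or Visit 4 are mapped. In SAP 3.4.1.1, state whether the cut-off for weekly WI-NRS scores is the termination visit or the end of the diary.

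The cost is a few tables, a short pooling program and some SAP text. Response rates will be lower in (2), and fewer subjects contribute in (3). No new data are collected.

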# 4.4.7.3 Planned Interim, Primary, and Final Analyses and Data Monitoring

To address business needs, an interim analysis may be conducted after approximately 50% of randomized subjects have completed 4 weeks of randomized treatment. Only a limited number of study team members and senior management stakeholders comprising the internal DRT would review the results of the interim analysis of unblinded data from the Double-Blind Treatment Period. The interim analysis would evaluate the effect of EP547 on WI-NRS, select secondary endpoints, and safety.

The primary analysis will be conducted after the last subject randomized has completed the Double-Blind Treatment Period to determine whether the primary efficacy endpoint of change from baseline in WI-NRS at Week 6 is statistically significant. Details regarding the primary analysis procedures, including database lock and unblinding procedures, will be finalized prior to analysis.

The final analysis will be conducted when all randomized subjects have completed the Open-Label Extension Period or are discontinued from the study, and the final database is locked.

The Data Monitoring Committee (DMC) is an independent group of external experts who will review safety data during the conduct of the study, as outlined in the DMC charter. The DMC will make a determination of relatedness for all AEs with CTCAE Grade 3 or higher. The DMC will also meet on an ad hoc basis when at least 3 AEs of CTCAE Grade 3 or higher have accrued or when there has been a single CTCAE Grade 4 or higher. Based on review of the data, the DMC will provide recommendations to the Sponsor on whether the nature, frequency, and/or severity of AEs associated with study drug warrant modification to the study protocol, suspension of dosing, or study termination.

# 4.4.7.4 Multicenter Studies

This is a multicenter study to be conducted globally. Efficacy data collected from all study sites will be pooled for data analysis. The effect of study site on the efficacy analysis results may be explored post-hoc, as needed.

# 4.4.7.5 *Multiple Comparisons/Multiplicity*

This is the first study to explore the efficacy of EP547 for more than 7 days. The familywise error rate will be controlled for the primary efficacy endpoint at an alpha of 5%. All other efficacy endpoints will be tested at the 0.05 level of significance without multiplicity adjustment.

# 4.4.7.6 Use of an "Efficacy Subset" of Subjects

The primary efficacy analysis will be performed on the Full Analysis Set; the Per Protocol Set will be utilized as a sensitivity analysis. The Per Protocol Set will exclude subjects with protocol deviations that might impact the assessment of efficacy measurements.

### 4.4.7.7 Active-Control Studies Intended to Show Equivalence

This study does not include an active-control product and is not intended to demonstrate equivalence between any two drug products.

